## 2. PROTOCOL SYNOPSIS

Title of Study: A Phase 2 Randomized, Double-Blind, Placebo-Controlled, Parallel-Cohort Study to Evaluate the Efficacy, Safety, Tolerability, and Pharmacokinetics of Once-Daily Application of Topical VDA-1102 Ointment for 28 Days in Subjects with Actinic Keratosis	
Study Center(s): Approximately 6 sites in the US and 3 in Israel	
Study Duration: 11 months	Phases of Development: Phase 2
Study Objectives:	

Primary Objective: To compare the reduction on Day 56 in the number of the actinic keratosis (AK) lesions in the Treatment Field of subjects receiving once-daily topical 5% or 10% VDA-1102 ointment for 28 days to the reduction in the number of AK lesions in subjects receiving placebo.
	
Secondary Objectives:	

 
• To evaluate the systemic and local (skin) safety and tolerability of once-daily topical application of 5% or 10% VDA-1102 ointment or placebo for 28 days in adult subjects with AK.
 
• To assess the systemic exposure of VDA-1102 and jasmonic acid, its primary metabolite, at selected time points during topical application of 5% or 10% VDA-1102 ointment or placebo for 28 days in adult subjects with AK.
 
	
Exploratory Objectives:	

 
• To compare the proportion of subjects receiving 28 days of 5% or 10% VDA-1102 who on Day 56 had complete clearance of AK lesions to subjects receiving placebo.
 
• To compare the reduction on Day 84 in the number of the actinic keratosis (AK) lesions in the Treatment Field of subjects receiving once-daily topical 5% or 10% VDA-1102 ointment for 28 days to the reduction in the number of AK lesions in subjects receiving placebo.
 
	
Study Design:	

This Phase 2 clinical trial is a multi-center, randomized, double-blind, placebo-controlled, multiple-dose, parallel-cohort study involving the once-daily non-occluded, topical dermal application of the study drug (5% or 10% VDA-1102 ointment, or placebo) for 28 days.
	

Approximately 84 subjects will be enrolled in this study in order to obtain at least 75 evaluable subjects by the end of the trial. Fifteen (15) of these subjects will constitute a Nested Phase 1b Safety Study Sub-Cohort, and a maximum of 18 of the 84 subjects will be included in a PK Study Sub-Cohort. These 2 sub-cohorts may overlap and are described below.
	

To qualify for the study, subjects aged 18 (inclusive) or older must have signed informed consent and met the study enrollment criteria that include having 4-8 discrete Grade 1 or 2 AK
	

lesions within a 25 cm^2 area on the scalp or face ("the Treatment Field"). Subjects will be randomly assigned in a double-blind fashion to 1 of 3 parallel treatment cohorts (5%, or 10% VDA-1102, or placebo, respectively) in a ratio of 1:1:1. Randomized subjects will apply a single thin application of the study drug to their Treatment Field for 28 days.

This clinical trial will include 3 study periods.

***Screening Period (Day -21 through Day 1 Pre-Dose):***

During the **Screening Visit** (up to 21 days pre-dose) subjects who have given written informed consent will undergo safety assessments including medical and medication histories, adverse event (AE) documentation, vital signs, limited physical examination, clinical laboratory testing, 12-lead electrocardiograms (ECGs), dermatologic examination, and Treatment Field identification, as well as other qualifying procedures.

At the **Day 1 Pre-Dose Visit**, eligible subjects will return to the investigative site for baseline assessments as well as final eligibility screening. The 18 subjects enrolled in the PK Study Sub-Cohort (described below) will have a baseline blood sampling for PK analysis. Subjects who continue to meet the enrollment criteria will undergo randomization to 1 of 3 treatment groups: 5% VDA-1102, 10% VDA-1102, or placebo.

Three times during the Screening and Day 1 Pre-Dose Visits, subjects will be trained and tested in proper application of the study drug to the Treatment Field with the help of a flexible plastic stencil ("Treatment Field Template"). Subjects unable to apply the study drug properly will be excluded, unless they are accompanied by a dosing partner willing and able to properly dose the subject each evening.

***Treatment Period (Day 1 Dosing through Day 28):***

During the **Day 1 Dosing Visit**, randomized subjects (or their dosing partner) will apply the first dose of the study drug under the supervision of the site personnel in order to further assure proper application.

From Day 1 through Day 27, subjects will continue dosing the study drug to their respective Treatment Fields each evening while at home. Subjects will visit their respective investigative sites on **Day 7 and Day 14** for safety and efficacy assessments, drug accountability, and re-training in proper application of the study drug. In addition, subjects in the PK Study Sub-Cohort will undergo a single blood sampling at approximately 12 h after the prior evening's dose. On the **Day 28 Visit**, subjects will return to the clinic for safety and efficacy assessments. Subjects in the PK Study Sub-Cohort will have timed blood samples taken at approximately 12, 15, 18 and 21 hours after their Day 27 evening dose and a 24-hour Holter monitor will be attached.

During the Treatment Period, site personnel will communicate once-weekly with each subject in order to assure study drug compliance, review dosing instructions, and remind subjects of their next study visit.

**Observation Period (Day 29 through 84):**

Subjects will visit their respective investigative site on **Days 35 and 56** for efficacy and safety assessments. On **Day 84** subjects will return to the sites for their final efficacy and safety assessments. Subjects with continuing AEs will be scheduled for follow-up evaluation, as appropriate.

**Nested Phase 1b Safety Sub-Cohort:** The first 15 (PK and non-PK) subjects enrolled in the trial will undergo on Day 7 the safety examinations planned for all other subjects plus physical examination, clinical laboratory and ECG assessments. Once all 15 subjects in this Nested Phase 1b Safety Sub-Cohort have completed their Day 7 Visit, safety data (including AEs, LSR scores, clinical laboratory results, and ECG data) from Day 1 through Day 7 will be reviewed in a blinded fashion by a safety committee. During this blinded interim safety review, enrolled subjects will continue dosing the study drug and study enrollment will remain open.

**PK Study Sub-Cohort:** Of the approximate 84 subjects to be enrolled in this trial, a maximum of 18 subjects at select sites will undergo blood sampling for PK analysis on Day 1 Pre-Dose as well as on Days 7, 14, 28, and 35. In addition, the PK Study Sub-Cohort will undergo 24-hour cardiac Holter monitoring on Day 28. Subjects included in this Sub-Cohort may also be included in the Nested Phase 1b Safety Sub-Cohort if they are in one of the first 15 subjects to be enrolled into the study.

**Number of Randomized Subjects (planned):** Approximately 84 (3x28) subjects will be randomized in order to complete the study with at least 75 (3x25) subjects anticipated to be available for efficacy analysis.

**Maximum Time Subjects May Remain in the Study:** Subjects may participate in this study for a maximum of approximately 117 days (21 Screening Period + 32 Treatment Period + 64 Observation Period)

**Study Endpoints:**

**Primary Efficacy Endpoint:** Change from baseline in the number of AK lesions in the Treatment Field of each subject on Day 56.

**Safety Endpoints:** Assessment of AEs, vital signs, physical examinations, clinical laboratory parameters, Local Skin Reaction (LSR) Scores, and electrocardiograms.

**Pharmacokinetic Endpoints:** Assessment of the systemic exposure of VDA-1102 and its primary metabolite jasmonic acid at selected time points during topical application of 5% or 10% VDA-1102 ointment for 28 days in adult subjects with AK.

**Exploratory Endpoints:** The percentage of subjects achieving complete clearance of AK lesions within the Treatment Field on Day 56.

Change from baseline in the number of AK lesions in the Treatment Field of each subject on

Day 84.

### **Statistical Analyses:**

#### ***Efficacy Analysis***

Efficacy analysis will be based on changes from baseline to Day 56 in AK lesions. Comparative analysis of the changes will be applied between each of the active groups versus the placebo group using the two-sample t-test or non-parametric Wilcoxon-Mann-Whitney rank sum test for independent samples or Median test (as is appropriate). In the event that the number of baseline lesions is different between the treatment groups, then relative changes (%) will be analyzed as well.

The overall change and the trend of differences in the changes over time between the groups will be analyzed using mixed-effect model for repeated measures. The model will include changes at any time, the fixed effect time and the interaction of treatment and time. The model will be adjusted for baseline measures and for other relevant covariates.

#### ***Interim Efficacy Analysis (IEA)***

A single interim efficacy analysis will be conducted as soon as 50% of the subjects have completed their Day 56 Visit. The objective of the IEA is to evaluate the probability of achieving the primary efficacy endpoint at the conclusion of the study. The unblinded data for the interim analysis sub-set will be analyzed by an independent statistician.

The result of the IEA will be a calculated effect size and t-value, which will be based on the difference in the change from baseline in the number of AK lesions for each of the active groups as compared to the placebo group. If baseline measure differs between the groups, then relative change (%) will be tested. The total significance level of 5% was divided between the interim efficacy analysis (0.005) and the final analysis (0.045). The spending function calculation for alpha will be performed using the O'Brien-Fleming methods. In case the distribution of the outcome variable does not approximate normality, the appropriate non-parametric methods will be considered for the interim analysis.

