#### 12.1.3 Unblinding

In the event of an emergency, the Investigator (or designee) should contact the Study Medical Monitor to discuss the case before unblinding of an individual subject's treatment code is broken by the site. If the medical condition of the subject warrants immediate unblinding, the treatment assignment of the subject may be obtained from the IRT without first consulting the Study Medical Monitor. However, the site must contact the Study Medical Monitor as soon as possible after the unblinding.

An interim efficacy analysis will be performed after approximately 50% of the enrolled subjects have completed their Day 56 Visit and their data have been recorded. The single pre-designated unblinded statistician described above in Section 12.1.2 will perform this analysis. The specifics of this interim analysis will be included in the Statistical Analysis Plan.

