## 17. STATISTICAL PLAN

### 17.1 Sample Size Rationale and Justification

The primary objective of the trial is to compare the reduction on Day 56 in the number of the AK lesions (or % reduction if baseline measure will be found different between the groups) in the Treatment Field of subjects receiving 5% or 10% VDA-1102 ointment to the reduction in the number of AK lesions in subjects receiving placebo. The sample size calculation was based on demonstrating an effect size of 0.83 using a two group t-test with a 0.045 two-sided significance level. The total significance level of 5% was divided between the interim analysis 0.5% (0.005) and the final analysis 4.5% (0.045). The sample size calculation was based on the final significance. The spending function calculation for alpha will be performed using the O'Brien-Fleming approach. Assuming a drop-out rate of 10%, approximately 84 subjects will be recruited in order to complete the study with a sample of approximately 75 evaluable subjects.

A sample size of 25 in each group will have 80% power to detect an effect size of 0.83 using a two group T-test with a 0.045 two-sided significance level.

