### 17.4 Interim Efficacy Analysis

An interim efficacy analysis will be conducted as soon as approximately 50% of the subjects have completed the study. The objective of the interim analysis is to evaluate the probability to achieve the primary efficacy endpoint.

The data for the interim analysis sub-set will be collected and analyzed for effect size and t-value. Effect size will be calculated based on the difference in the change from baseline in AK lesions for each of the active groups as compared to the placebo group. Relative change (%) will be used if baseline measure will be found different between the groups.

Futility will be based on O'Brien-Fleming boundaries. If the t-value with 22 degrees of freedom is below 0.34, then the study is unlikely to succeed when taken to completion. In case the distribution of the outcome variable will not be found with approximation to normality, then appropriate non-parametric methods will be considered for the interim analysis.

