## 3. SCOPE

- 3.1 This document applies to all members of the statistical & data management units in Medistat Ltd.
- 3.2 This document includes both the main study trial analysis and interim analyses when applicable.

MediStat Statistics in Medicine	DOCUMENT NUMBER: 029-BST-PLN-001	PAGE: 8 of 45
TITLE: Statistical Analysis Plan for study:  A Phase 2 Randomized, Double-Blind, Placebo-Controlled, Parallel-Cohort Study to Evaluate the Efficacy, Safety, Tolerability, and Pharmacokinetics of Once-Daily Application of Topical VDA-1102 Ointment for 28 Days in Subjects with Actinic Keratosis	EFFECTIVE DATE : 22/MAY/2017 REVISION NUMBER : 2.0	

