#### 5.3.2 Sample Size Justification

5.3.2.1 The primary objective of the trial is to compare the reduction on Day 56 in the number of the AK lesions (or % reduction if baseline measure will be found different between the groups) in the Treatment Field of subjects receiving 5% or 10% VDA-1102 ointment to the reduction in the number of AK lesions in subjects receiving placebo. The sample size calculation was based on demonstrating effect size of 0.83 using a two group t-test with a 0.045 two-sided significance level. The total significance level of 5% was divided between the interim analysis 0.5% (0.005) and the final analysis 4.5% (0.045). The sample size calculation was based on the final significance. The spending function calculation for alpha will be performed using the O'Brien-Fleming approach. Assuming a drop-out rate of 10%, approximately 84 subjects will be recruited in order to complete the study with a sample of approximately 75 evaluable subjects.

5.3.2.2 A sample size of 25 in each group will have 80% power to detect an effect size of 0.83 using a two group T-test with a 0.045 two-sided significance level.

	DOCUMENT NUMBER: 029-BST-PLN-001	PAGE: 22 of 45
TITLE: Statistical Analysis Plan for study: A Phase 2 Randomized, Double-Blind, Placebo-Controlled, Parallel-Cohort Study to Evaluate the Efficacy, Safety, Tolerability, and Pharmacokinetics of Once-Daily Application of Topical VDA-1102 Ointment for 28 Days in Subjects with Actinic Keratosis	EFFECTIVE DATE : 22/MAY/2017 REVISION NUMBER : 2.0	

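### Minor: the plan names O'Brien-Fleming spending but writes the leftover increment 0.045 as the level of the final t-test (about 0.048 would match), and does not say what the interim 0.005 is for

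*Protocol*

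**What the plan says.** The split of 5% into 0.005 and 0.045 stands in the protocol synopsis ("The total significance level of 5% was divided between the interim efficacy analysis (0.005) and the final analysis (0.045"), in Protocol 17.1 and in the SAP: "The total significance level of 5% was divided between the interim analysis 0.5% (0.005) and the final analysis 4.5% (0.045" (SAP 5.3.2). All three places name O'Brien-Fleming. Protocol 17.1 has: "The spending function calculation for alpha will be performed using the O'Brien-Fleming approach". The sample size in Protocol 17.1 and SAP 5.3.2 is then set "using a two group t-test with a 0.045 two-sided significance level", for an effect size of 0.83, 25 per arm and 80% power.

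On the purpose of the look, the synopsis says: "The objective of the IEA is to evaluate the probability of achieving the primary efficacy endpoint at the conclusion of the study". The one numerical interim rule in either document is for futility: "If the t-value with 22 degrees of freedom is below 0.34, then the study is unlikely to succeed when taken to completion" (Protocol 17.4).

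Protocol 12.1.3 defers the details: "The specifics of this interim analysis will be included in the Statistical Analysis Plan". SAP section 3 says: "This document includes both the main study trial analysis and interim analyses when applicable". The SAP repeats the split in 5.3.2 and, in 5.2.5.4, refers back to the interim analysis of the protocol. It has no interim section, boundary or decision rule.

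**The concern.** A spending increment and a nominal test level are different quantities. The increment is the extra type I error used at a look, after allowing for what earlier looks have used. The nominal level is the p-value threshold applied at that look. The interim and final statistics are positively correlated, so the nominal levels of a two-look design can sum to more than 5% while the total error stays at 5%. The plan names a method that exploits this, then writes the simple remainder as the test level.

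Two things are at stake. First, 0.045 is the only final level written anywhere, so a final p-value between 0.045 and about 0.048 would be read as non-significant, or argued over after unblinding. Second, the correct final level depends on what 0.005 is for. An efficacy boundary at the look leads to about 0.048. A look for futility only leads to 0.050. The documents do not say which applies. If 0.005 is an efficacy boundary, they do not say what follows from crossing it.

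**Working it through.** **Inputs.** Total two-sided alpha 0.05, split 0.005 and 0.045 (synopsis; Protocol 17.1; SAP 5.3.2). Effect size 0.83, 25 per arm, 80% power, 10% drop-out, 75 evaluable, 84 recruited (Protocol 17.1). One look at 50% of subjects (synopsis). Futility threshold at 22 degrees of freedom (Protocol 17.4), which means 12 per arm in a two-arm comparison, or 12/25 = 48% of the information.

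**1. The plan's own figures.** Noncentrality = 0.83 × √(25/2) = 2.934, with 48 degrees of freedom and a critical value of 2.058 at 0.045 two-sided. Power from the noncentral t is 80.7%. With 24 per arm it is 79.0%, so 25 is the smallest sufficient number. 75/0.9 = 83.3, rounded up to 84. The stated figures reproduce.

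**2. Error spent by the written pair.** Under the null, Z1 and Z2 are bivariate normal with correlation √t, where t is the information fraction.

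P(|Z1| > 2.807 or |Z2| > 2.005) at t = 0.50 is 0.0470.

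It is 0.0476 at t = 0.40, 0.0471 at t = 0.48 and 0.0464 at t = 0.60. If the look cannot reject for efficacy, at most 0.045 is spent.

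**3. The matching final level.** Solve for the final level that makes the total 0.05:

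| Rule | Interim level | Final level |
|---|---|---|
| Interim fixed at 0.005, t = 0.50 | 0.005 | 0.0481 |
| Classical O'Brien-Fleming, t = 0.50 (c = 1.977) | 0.0052 | 0.0480 |
| Lan-DeMets, 0.025 per side, t = 0.50 | 0.0031 | 0.0490 |
| Lan-DeMets, two-sided form, t = 0.50 | 0.0056 | 0.0478 |
| Interim fixed at 0.005, t = 0.40 | 0.005 | 0.0474 |
| Interim fixed at 0.005, t = 0.48 | 0.005 | 0.0480 |
| Interim fixed at 0.005, t = 0.60 | 0.005 | 0.0487 |

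The classical boundary leaves an increment of 0.05 − 0.0052 = 0.0448. The plan's 0.005 and 0.045 therefore agree with it as increments. They do not agree with it as nominal levels, because the final nominal level is 0.0480.

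**4. Check with t-tests.** These levels rest on normal theory. In simulations of actual t-tests at 12 then 25 per arm (2 million runs, standard error about 0.00015), 0.005 with 0.045 spends 0.0474 to 0.0475, and 0.005 with 0.0481 spends 0.0504 to 0.0505.

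**5. Cost in power** (final test only, 0.83, 25 per arm). 80.7% at 0.045, 81.5% at 0.048, 82.0% at 0.050. The loss is 81.5 − 80.7 = 0.8 points, or 82.0 − 80.7 = 1.3 points if the look is for futility only.

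**6. What 0.005 would mean as an efficacy boundary.** |t| > 3.12 at 22 degrees of freedom, crossed with probability 17% if the true effect is 0.83.

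**7. Trial-wide error.** Two doses are each compared with placebo without adjustment. With equal arms and no effect in either dose, simulation of both looks gives a chance of at least one false positive of about 0.087 with 0.005/0.045. It is about 0.092 with 0.005/0.048, and about 0.091 with a futility-only look and a final 0.05.

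**The case against.** The strongest reply is that nothing is miscalculated: 0.005 and 0.045 sum to 0.05, a Bonferroni split is valid, error per comparison is controlled, and sample size and power hold. All of that stands. The reply does not explain why the text attributes the final level to O'Brien-Fleming, since no form of that method computed here at a 50% look gives 0.045.

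A second reply is that 0.045 is only a sample-size input. The efficacy sections (Protocol 17.2.1, SAP 5.6.5) state no test level, and the spending calculation is described as still to be done. This stands in part. A reader might infer that the plan declares a final p between 0.045 and 0.048 a failure. No document says so. The supportable statement is that 0.045 is the only final level written, so such a result would probably be read as non-significant or be contested.

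Third, the single value 0.048 depends on the form of O'Brien-Fleming and is slightly liberal with t-tests of this size. Both are true, so the final level should be computed, not copied to four decimals.

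Fourth, the effect is small beside the choice among t-test, Wilcoxon, Median test and ANCOVA in three populations. That is fair, and is why the point is minor.

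**Conclusion.** The point holds as a minor inconsistency. The written final level does not follow from the named method, and the purpose of 0.005, which decides the right level, is not stated. Per dose-versus-placebo comparison the plan spends about 0.047 of its 0.05, or at most 0.045 if the look is for futility only, and gives up 0.8 to 1.3 points of power.

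Three stronger readings are not supported. Type I error is not inflated for a single comparison by this split. The sample size is not wrong. Nor can the plan be called conservative as a whole: that word applies per comparison only, because two unadjusted doses bring the trial-wide error to about 0.087. That excess comes from testing two doses, not from the 0.005/0.045 split.

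The figures assume information proportional to subjects, equal arms and a look near 50%. The synopsis times the look by Day 56 Visits and Protocol 17.4 by study completion. Between 40% and 60% information, with the interim at 0.005, the matching final level stays within 0.0474 to 0.0487.

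**What to change.** Amend the synopsis, Protocol 17.1 and SAP 5.3.2, and add a short interim paragraph to the SAP. Choose one option:

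- **(a) Efficacy boundary.** State that 0.005 is the interim efficacy boundary and what crossing it leads to. Set the final level by the named O'Brien-Fleming method, form specified, at the actual information fraction (about 0.048 at 50%). Note that the normal-theory value gives about 0.0504 with t-tests at 12 then 25 per arm. Compute the two levels as a pair: 0.005 with a final 0.0492, which belongs to a different interim level at 40% information, would spend 0.0517.
- **(b) Futility only.** State in the synopsis and Protocol 17.4 that the look is non-binding futility, assign it no alpha, and test the final at 0.05 per comparison.
- **Otherwise,** keep 0.045, call it a Bonferroni split and drop the O'Brien-Fleming wording on alpha.

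Under any option, state that the 5% applies per comparison and does not control the trial-wide error (about 0.087 as written, about 0.091 to 0.092 under (a) or (b)).

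The change should be made before database lock by staff blinded to interim results; SAP 5.2.5.4 places the unblinded statistician at the firm that issued the SAP. It costs wording only: 25 per arm, 75 evaluable and 84 recruited are unchanged. Option (b) gives up an early efficacy claim for which no rule is written now.
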